4.4. Baseline and Postbaseline Definition

Table 5 describes the rules for determining the patient population and baseline and postbaseline observations for study and type of analysis.

Table 5. Patient Population with Baseline and Postbaseline Definitions by Type of Analysis

Study Period/Analysis	Patient Population	Baseline Observation	Postbaseline Observation(s)
Treatment Period			
Primary Efficacy analyses	ITT Population with a baseline and at least 1 postbaseline observation	Visit 3	Visit 13
TEAEs	Safety Population	All Visits 1-3	All Visits 3.01-14
Serious Adverse Events, Discontinuations due to Adverse Events	Safety Population	N/A	
C-SSRS analyses	Patients with a baseline and at least 1 postbaseline C-SSRS assessment	All Prior History: Visits 1-3 including	All Visits 3.01-14
Treatment-emergent abnormal laboratory values	Safety Population with normal laboratory values at all nonmissing baseline visits (with respect to direction being analyzed) and who have at least 1 postbaseline observation	Low: Minimum from Visits 1-3 High: Maximum from Visits 1-3 Abnormal: All Visits 1-3	Low: Minimum from Visits 3.01-14 High: Maximum from Visits 3.01-14 Abnormal: All Visits 3.01-14
Treatment-emergent immunogenicity	Safety Population	Visit 3	All Visits 3.01-14
Treatment-emergent changes in temperature and weight	Safety Population with a baseline and at least 1 postbaseline observation	Low: Minimum from Visits 1-3 High: Maximum from Visits 1-3	Low: Minimum from Visits 3.01-14 High: Maximum from Visits 3.01-14
Treatment-emergent changes in blood pressures, pulse, and ECGs	Safety Population with a baseline and at least 1 postbaseline observation	Low: Last nonmissing from Visits 1-3 High: Last nonmissing from Visits 1-3	Low: Minimum from Visits 3.01-14 High: Maximum from Visits 3.01-14
Continuous safety analyses	Safety Population with a baseline and at least 1 postbaseline observation	Last of Visits 1-3	All scheduled visits 3 < Visits ≤ 14

ECGs = electrocardiograms; eCRF = electronic case report form; ITT = intent-to-treat; N/A = not applicable; TEAEs = treatment-emergent adverse events

Note: Visit 3.01 indicates the first unscheduled visit occurring after Visit 3 and prior to Visit 4.

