3.6.3 Safety Variables

- Hematology, blood chemistry and urinalysis at Visits 1, 3, 6, 9, 12, 13 and 14 or Early Termination. See Section Appendix 1 for a complete list of laboratory tests to be done.
- ECG evaluation at Visits 1, 3, 6, 9, 12, 13 and 14 or Early Termination
- Complete physical examination at Visits 1, 3, 6, 9, 12, 13 and 14 or Early Termination
- Vital signs (sitting blood pressure, pulse, breathing, and temperature) and weight will be measured at all visits.
- MRI Scan of the brain at Visit 1, 9, 13 and 14 or Early Termination.
- C-SSRS at Visit 3, 6, 9, 12, 13, and 14 or Early Termination
- Data regarding AEs and concomitant medications will be collected at all visits

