4.4 Early Termination Visit

If a subject will drop-out the study before Visit 14 (Week 52), the clinical site will try to schedule an early termination visit. During this visit, the following assessments and procedures should be performed:

- The following questionnaires will be completed: ADAS-Cog (see Appendix 2), MMSE (see Appendix 3), CDR-SOB (see Appendix 4). NPI (see Appendix 5), GDS (see Appendix 6), ADCS-ADL (see Appendix 7) and C-SSRS (see Appendix 8).
- Measure vital signs (sitting blood pressure, pulse, breathing, and temperature) and weight.
- Perform a complete physical examination.
- Measure 12-lead ECG.
- Record any changes in concomitant medications.
- Record any adverse events, if applicable.
- Collect blood and urine samples for hematology, serum chemistry, pregnancy test (only for women of childbearing potential), biomarker analysis and urinalysis.
- Perform MRI scan including FLAIR and T2- weighted gradient-echo sequences.

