4.8. Safety Analyses

The safety and tolerability of treatment will be assessed by summarizing the following:

- AEs
- Treatment-emergent adverse events (TEAEs)
 - By PT
 - By SOC
 - By maximum severity
 - By considered to be related to investigational produce by investigator
- Serious Adverse Events (SAEs)
- AE leading to discontinuation
- Suicide-Related Thoughts and Behaviors
- Vital signs and weight
- Laboratory measurements
- Electrocardiograms (ECGs)

All safety analyses will be based on the safety population. AE rates will be summarized by treatment group and overall, and will be broken down by severity, seriousness and relation to study drug. Change of MRI, C-SSRS, physical examinations, vital signs, ECG

and standard laboratory results will be summarized with means, standard deviations, medians and ranges for continuous variables and with counts and percentages for categorical variables. Statistical tests are not planned for safety.

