4.8.1. Adverse Events

An AE is defined as any untoward medical occurrence in a subject who is administered a medicinal product and that does not necessarily have a causal relationship to the treatment. All AEs will be included in the data listings. Verbatim terms on case report forms will be mapped to preferred terms and system organ classes (SOC) using the Medical Dictionary for Regulatory Activities (MedDRA) (version 19.1).

A Treatment Emergent Adverse Event (TEAE) is defined as an adverse event that occurs on or after the treatment dose. TEAE summary will be displayed by treatment. Unless otherwise specified, summaries that are displayed by SOC and preferred terms will be ordered alphabetically by SOC, and within each SOC, preferred terms will also be ordered alphabetically. Summaries of the following types will be presented:

- Subject incidence of TEAEs by MedDRA SOC and preferred term.
- Subject incidence of TEAEs by MedDRA SOC, preferred term, and severity. Severity will be recorded as deemed by investigator. At each level of subject summarization, a subject is classified according to the highest severity if the subject reported one or more events.
- Subject incidence of study drug related TEAEs by MedDRA SOC and preferred term.
- Subject incidence of TEAEs by descending incidence of preferred terms.
- Subject incidence of serious TEAEs by MedDRA SOC and preferred term, if applicable.
- Subject incidence of TEAE leading to early termination by MedDRA SOC and preferred term, if applicable.

For each subject and for each adverse event, the duration of the event will be calculated as:

$$\text{Duration of AE} = \text{AE stop date} - \text{AE start date} + 1$$

The duration of AEs will be displayed in the data listing.

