As guidance for determination of important medical events see the ‘WHO Adverse Reaction Terminology – Critical Terms List’. These terms either see or might be indicative of a serious disease state. Such reported events warrant special attention because of their possible association with a serious disease state and may lead to more decisive action than reports on other terms.

4.8.3. *Clinical Laboratory Evaluation*

Abnormal laboratory findings without clinical significance (based on the investigator's judgment) should not be recorded as adverse events; however, laboratory value changes requiring therapy or adjustment in prior therapy are considered adverse events. Adverse events will be reviewed continuously throughout the study.

Laboratory results (hematology, serum chemistry and urinalysis) will be presented in data listing. Abnormal values will be flagged as high or low relative to the local lab normal ranges, where applicable. Values that are deemed as abnormal, clinically significant will also be flagged.

Laboratory results will be summarized using descriptive statistics at baseline and post-dose. Changes from baseline will also be summarized. Only non-missing assessments at baseline and post-dose will be analyzed.

Any clinically significant lab abnormalities will be determined by the Principal Investigator and will be reported in the AE table summaries.

4.8.4. *Suicide-Related Thoughts and Behaviors*

Suicidal ideation, suicidal behavior, and self-injurious behavior without suicidal intent occurring during treatment, based on the C SSRS, will be summarized by treatment. In particular, for each of the following events, the number and percent of patients with the event will be enumerated by treatment: completed suicide, nonfatal suicide attempt, interrupted attempt, aborted attempt, preparatory acts or behavior, active suicidal ideation with specific plan and intent, active suicidal ideation with some intent to act without specific plan, active suicidal ideation with any methods (no plan) without intent to act, nonspecific active suicidal thoughts, wish to be dead, and self-injurious behavior without suicidal intent.

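### The suicide-event table draws only on the C-SSRS and only on subjects with a postbaseline C-SSRS, so it can miss a suicide that the SAE table shows

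*SAP*

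**What the plan says.** **Source and content of the table.** SAP 4.8.4 says that suicidal ideation, suicidal behavior and non-suicidal self-injury "occurring during treatment, based on the C SSRS, will be summarized by treatment". It then specifies that "the number and percent of patients with the event will be enumerated by treatment: completed suicide, nonfatal suicide attempt" and a series of lesser categories. Three composites follow: suicidal behavior, suicidal ideation, and either of the two. No source other than the C-SSRS is named.

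**Population.** SAP 4.4, Table 5, gives the population for C-SSRS analyses as "Patients with a baseline and at least 1 postbaseline C-SSRS assessment". Every other safety row in Table 5 starts from the Safety Population, some with an added requirement for baseline or postbaseline data. SAP 4.8 lists suicide-related thoughts and behaviors among the safety assessments and then states: "All safety analyses will be based on the safety population".

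**Timing.** Protocol 3.6.3 schedules "C-SSRS at Visit 3, 6, 9, 12, 13, and 14 or Early Termination", that is, baseline at Week 0 and then Weeks 6, 12, 18, 30 and 52. After withdrawal, Protocol 4.4 says only that "the clinical site will try to schedule an early termination visit".

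**Other reporting of the same events.** SAP 4.8.1 plans "Subject incidence of serious TEAEs by MedDRA SOC and preferred term, if applicable", and Table 5 assigns serious adverse events to the Safety Population.

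**The concern.** Completed suicide is the first event the table is meant to count, yet entry to the table depends on an assessment that a person who has died cannot attend. If the C-SSRS is the only source and one postbaseline C-SSRS is required, the chance of being counted depends on the outcome itself. The same gap carries into the suicidal-behavior composite and the combined ideation-or-behavior composite.

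The report could then show no suicides in its dedicated table and a death by suicide among the serious adverse events, with nothing in the SAP to reconcile the two. With about 11 subjects per arm, one case is the whole signal. Separately, the Table 5 row and SAP 4.8 give two denominators for the same table, and that needs settling even if no event occurs.

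**Working it through.** The plan gives no suicide rate, power or formal sample size, so there is no figure to reproduce. The check sets the rules against the visit schedule and then works one hypothetical case.

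**Inputs**
- C-SSRS weeks: 0 (baseline), 6, 12, 18, 30, 52 (Protocol 3.6.3 with the visit list).
- Infusions before the first scheduled postbaseline C-SSRS: Weeks 0, 2 and 4 (Protocol 4.2.1 to 4.2.3).
- Arm size: about 11 (SAP 3.2).
- Missing values: not imputed (SAP 4.5 and 4.10).
- Assumption: one suicide in an arm of 11. This is an illustration, not an expected rate.

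**Step 1. Gaps between scheduled assessments.** 6 − 0 = 6, 12 − 6 = 6, 18 − 12 = 6, 30 − 18 = 12 and 52 − 30 = 22 weeks. The period with no scheduled postbaseline C-SSRS is Weeks 0 to 6, or 6/52 = 11.5% of follow-up.

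**Step 2. What one event does to the table**

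| Event | C-SSRS completed after the event? | Table under SAP 4.4 and 4.8.4 | True count |
|---|---|---|---|
| Suicide before the first postbaseline C-SSRS | No | 0/10 | 1/11 |
| Suicide after at least one postbaseline C-SSRS | No | 0/11 | 1/11 |
| Suicide at any time | Yes, form completed after the death | 1/11 | 1/11 |
| Nonfatal attempt, further C-SSRS done | Yes | 1/11 | 1/11 |
| Nonfatal attempt, no further C-SSRS | No | 0/10 or 0/11 | 1/11 |

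All rows assume that the other 10 subjects each have a postbaseline C-SSRS. In the last row, 0/10 applies if the subject never had a postbaseline C-SSRS, and 0/11 if one was done before the attempt.

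**Step 3. Proportions with exact (Clopper-Pearson) 95% limits**
- 1/11 = 9.1%. Lower limit 1 − 0.975^(1/11) = 0.2%; upper limit, the 0.975 quantile of Beta(2, 10), = 41.3%.
- 0/10 = 0%. Upper limit 1 − 0.025^(1/10) = 30.8%.

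The intervals overlap widely, as they must at this size. What changes is whether the table shows an event at all.

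**Step 4. Whether the SAE record is a firm back-up.** Protocol 7.3 first requires reporting of serious events after the first dose and during follow-up. It then says that reporting runs to 30 days after the last dose, about Week 18 + 30/7 = Week 22.3, with later reporting for events judged related or of unknown relationship. Both statements cover Weeks 0 to 6. For the later follow-up they differ and must be reconciled.

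**The case against.** Several counter-arguments are sound, and they limit the point.

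- **Any postbaseline C-SSRS qualifies.** A reader might infer that only subjects interviewed after the event are counted. Table 5 does not say that. An assessment before the event is enough to stay in the denominator, and Table 5 also counts unscheduled visits from 3.01 onward. Week 6 is the first scheduled assessment, not the earliest possible one.
- **The form can record a death.** A reader might infer that a suicide always removes its own case, or that the row is zero by construction. The Since Last Visit version in Protocol Appendix 8 has a suicide item and a lethality code for death, which a rater could complete without the subject. However, neither document tells staff to complete the form after a death, so capture is left to the site.
- **Survivors are normally captured.** A nonfatal attempt can be recorded at the next C-SSRS or at Early Termination. It is missed only if neither takes place.
- **The event is not hidden.** A reader might infer that a suicide could go unreported. Death is an SAE criterion, serious TEAEs are tabulated on the Safety Population, and SAP 4.8.1 lists all AEs. In a trial of 22 a suicide would be seen. The defect is one table that can contradict another.
- **Other Table 5 rows also require postbaseline data.** That is reasonable for a change or shift in a measurement. It does not suit a count of deaths, which can be known without a measurement.
- **A Safety Population denominator is wrong for ideation.** Subjects never interviewed would count as free of ideation, which dilutes the percentages. This objection stands, and the fix below leaves those rows where they are.

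**Conclusion.** The point holds in limited form. The SAP names one source for completed suicide and attempts, and restricts the table to subjects with a postbaseline C-SSRS, contrary to its own rule that all safety analyses use the Safety Population. Provided no C-SSRS form is completed after the event, a suicide before the first postbaseline assessment turns 1/11 into 0/10, and a later one turns 1/11 into 0/11. The first case can arise in the 11.5% of follow-up before Week 6, or for longer if the Week 6 assessment is missed.

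The conclusion rests on the text of SAP 4.4, 4.8 and 4.8.4 and on the absence of an instruction to complete the form after a death. The single case in 11 is an assumption, since the documents give no event rate. The loss is from the C-SSRS table and its composites, not from safety reporting as a whole. It does not touch the change-from-baseline summaries, for which the postbaseline condition is appropriate. It merits correction because the remedy is cheap and the two tables should not be able to disagree on a suicide.

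**What to change.** Amend SAP 4.4 (Table 5), 4.3.3 and 4.8.4 as follows.

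1. Base the completed-suicide, attempt and suicidal-behavior composite rows on the Safety Population. Count an event if it is recorded on the C-SSRS or in the AE, SAE or death record from the first infusion to Visit 14, with events found in more than one source counted once.
2. State in 4.3.3 that an AE or death record counts as a post-injection safety measurement. Otherwise a very early death could fall out of the Safety Population as well.
3. Keep the ideation rows and the change-from-baseline summaries on subjects with a postbaseline C-SSRS.
4. Apply the event sources in item 1 to the combined ideation-or-behavior composite and state its denominator. If it stays on the postbaseline C-SSRS subset, an early suicide is dropped again; on the Safety Population, a footnote should say that ideation is unknown for subjects never interviewed.
5. Show the number of subjects per arm with no postbaseline C-SSRS.
6. Reconcile the two statements of the SAE reporting period in Protocol 7.3, because the count to Visit 14 would draw on those records.

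With item 1 in place, the count of suicides no longer depends on whether a site completes a form after a death.

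The cost is a few sentences of SAP text, a reconciliation of C-SSRS with AE, SAE and death records for at most 22 subjects, and denominators that differ by row and need a footnote.

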4.2 Treatment Period

4.2.1 Visit 3: Baseline (Week 0)

Visit 3 will occur approximately 4 weeks after Visit 2. During this visit, the following assessments/procedures should be performed:

- The following questionnaires will be completed: ADAS-Cog (see Appendix 2), MMSE (see Appendix 3), CDR-SOB (see Appendix 4). NPI (see Appendix 5), GDS (see Appendix 6), ADCS-ADL (see Appendix 7) and C-SSRS (see Appendix 8).
- Measure vital signs (sitting blood pressure, pulse, breathing, and temperature) and weight.
- Perform a complete physical examination.
- Measure 12-lead ECG.
- Record any changes in concomitant medications.
- Record any adverse events, if applicable.
- Collect blood and urine samples for hematology, serum chemistry, pregnancy test (only for women of childbearing potential), biomarker analysis and urinalysis.
- Collect blood for IP and ship the packaging box containing the serum tubes to the lab designated by the sponsor (Please follow the serum for IP handling instruction separately provided by the sponsor).
- Administer the AstroStem in 220 mL of saline (two times of 10 ml AstroStem in 100 mL of saline) or the same volume of saline via I.V. for 2-6 hours to patients in the treatment group and the placebo group, respectively (Please see the detail procedures in Appendix 10).

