 - The client's general response
 - Your signature
16. Once the infusion of the second saline bag is finished, perform saline flush with approximate 20 cc of saline to make sure entire IP is administered.
17. Once the saline flush is finished, close the flow regulator of IV tubing. Apply gentle pressure over the insertion site with sterile gauze. Withdraw the needle. Hold pressure on the insertion site until bleeding stops. Cover the insertion site with an adhesive bandage.
18. Enclose empty two syringes of study drug and two IV bags into a pre-labeled bag and seal with tamper tale. Store at the secure place until a close-out visit.
19. A subject should stay in the infusion bed/chair at least 1 hour after infusion.
20. A subject will be discharged by PI's discharge order.

Monitoring Plan during and after the IV infusion of the study drug

1. Document the relevant data regarding infusion.
 - Record the start time of the infusion on the client's chart.
 - Include the date and time of the venipuncture
 - Specific name and location of the accessed vein
 - Flow rate
 - Type, length and gauge of the needle or catheter
 - The client's general response
 - Your signature
2. Check tubing for anything that might interfere with flow. Be sure clamps are in the open position.

3. Inspect the site for swelling, leakage at the site, coolness, or pallor, which may indicate infiltration. Ask if subject is experiencing any pain or discomfort. If any of these symptoms are present, the IV will need to be removed and restarted at another site.
4. Inspect the site for redness, swelling, and heat. Ask if patient is experiencing pain. The findings may indicate phlebitis. Notify principle investigator (PI) if phlebitis is suspected. IV will need to be discontinued and restarted at another site.
5. Check for local manifestations (redness, pus, warmth, induration, and pain) that may indicate an infection is present at the site or systemic manifestations (chills, fever, tachycardia, and hypotension) that may accompany local infection at the site. If signs of infection are present, discontinue the IV and notify PI.
6. If subject is experiencing shortness of breath and chest pain, discontinue the IV and notify PI. With PI's discretion, IV infusion will be terminated.

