2.1. Primary Objective

[Table 1](#) shows the primary objectives and endpoints used to determine the safety and efficacy of AstroStem in patients with Alzheimer's disease.

Table 1. Primary Objectives and Endpoints

Objectives	Endpoints

Primary Efficacy
 
• To evaluate the efficacy of AstroStem in patients with Alzheimer's disease 
Primary Safety
 
• To evaluate the safety of AstroStem in patients with Alzheimer's disease	
• Change of ADAS-Cog (Alzheimer's Disease Assessment Scale-cognitive subscale) from baseline (Visit 3) to Visit 13 (Week 30)• Number of subjects with treatment related adverse events as assessed by analysis of adverse events including symptoms, and abnormal findings on physical examination, vital signs, ECG, and standard laboratory examination results

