4.6. Treatment Group Comparability

4.6.1. *Patient Disposition*

Subject disposition information will be summarized for all subjects. Summaries will include: the number of subjects in each analysis population, the number of subjects completed the study, and the number of subjects discontinued study and its reason. All subjects randomized in the study will be included in the summary table. Patient allocation by investigator or site will be summarized. Patient allocation by investigator or site will also be listed as well.

4.6.2. *Protocol Deviations*

Listings of subjects with significant protocol deviations or violations will be provided. The following list of significant protocol violations will be determined from the clinical database and from the study clinical/medical group:

- Lack of informed consent or late informed consent
- Violations of inclusion/exclusion criteria
- Significant violations of prohibited concomitant medication usage as determined by the clinical/medical group
- Other significant protocol violations as determined by the clinical/medical group

4.6.3. *Patient Characteristics*

The following patient characteristics at baseline will be summarized by treatment group for all ITT patients:

- Demographic (age, gender, ethnic origin, height, weight, BMI)
- Medical history and Pre-existing condition

Medical history and pre-existing conditions will be summarized by preferred term (PT) within system organ class (SOC). Medical history is defined as illness(es) that ended prior to the signing of informed consent. Pre-existing conditions and AEs at baseline are those AEs occurring during the baseline/screening visits that is Visit 1, 2 and 3.

4.6.4. *Prior and Concomitant Therapy*

Verbatim terms on eCRFs will be mapped to Anatomical Therapeutic Chemical (ATC) class and Generic Drug Names using the World Health Organization (WHO) Drug Dictionary Enhanced (WHODDE) B2 format, March 1, 2015 release.

Prior medications are defined as medications started to take prior to the first injection. Concomitant medications are defined as medications started on or after the day of first injection of the study drug during the study.

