4.9. Interim Analysis and Data Monitoring

An unblinded interim safety analysis was done when there the first 4 subjects complete Visit 4 at Week 2 by an independent safety monitor. Change of vital sign, concomitant medications and adverse events(AEs) were evaluated to monitor the safety of the AstroStem.

Vital sign measured at Visit 3 and 4 were within normal ranges and no AEs were reported. In addition, all 4 subjects were found to be taking concomitant medications before and after administration of the treatment.

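### SAP Table 5 and Section 4.6.3 put the first-infusion visit in the adverse-event baseline, while Section 4.8.1 counts events from the dose onwards as treatment-emergent

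*SAP*

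**What the plan says.** Three places in the SAP bear on when an adverse event stops being a baseline event.

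- **Section 4.4, Table 5, TEAE row.** Baseline is Visits 1 to 3 and postbaseline is Visits 3.01 to 14. The table note explains that "Visit 3.01 indicates the first unscheduled visit occurring after Visit 3 and prior to Visit 4". The table is introduced as giving the rules for each type of analysis.
- **Section 4.6.3 (Patient Characteristics).** "Pre-existing conditions and AEs at baseline are those AEs occurring during the baseline/screening visits that is Visit 1, 2 and 3".
- **Section 4.8.1 (Adverse Events).** "A Treatment Emergent Adverse Event (TEAE) is defined as an adverse event that occurs on or after the treatment dose". The tables specified under this definition include "Subject incidence of study drug related TEAEs by MedDRA SOC and preferred term".

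Protocol 4.2.1 makes the first infusion, lasting 2 to 6 hours, a Visit 3 procedure. Protocol Appendix 10 adds that "A subject should stay in the infusion bed/chair at least 1 hour after infusion".

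The primary safety endpoint in SAP Section 2.1 is "Number of subjects with treatment related adverse events as assessed by analysis of adverse events including symptoms", together with abnormal examination, ECG and laboratory findings. It is not itself restricted to TEAEs.

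**The concern.** Visit 3 is both the baseline visit and the first dosing visit. Table 5 and Section 4.6.3 cut by visit and do not limit Visit 3 to its pre-dose part. Section 4.8.1 cuts at the dose. The two cuts disagree for events that start at Visit 3 once the infusion is under way, which is when a reaction to the first exposure would be seen. The protocol expects events of this kind: sites must check for infusion reaction, allergic reaction or anaphylaxis before each repeat injection (Protocol 4.2.2 to 4.2.6), and Appendix 10 sets out monitoring during and after the infusion.

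If the programmer follows Table 5, such an event is treated as baseline and leaves every TEAE table in Section 4.8.1, including the only table of drug-related events by preferred term. If the programmer follows Section 4.8.1, it stays. The choice affects how the primary safety result is presented, and the SAP does not make it.

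**Working it through.** The plan states no figure on this point, so the check is a comparison of texts followed by an illustration of size.

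**1. How the rules classify the same event**

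| Onset of the event | Table 5 (TEAE row) | Section 4.6.3 | Section 4.8.1 |
|---|---|---|---|
| Visit 3, before the infusion | Baseline | Baseline | Not a TEAE |
| Visit 3, during or after the infusion, assigned to Visit 3 | Baseline | Baseline | TEAE |
| After Visit 3 | Postbaseline | Not baseline | TEAE |

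Only the middle row conflicts. Visit 3.01 cannot be read as the post-dose part of Visit 3, because the note defines it as a separate unscheduled visit. The window in dispute lasts at least 2 + 1 = 3 hours to 6 + 1 = 7 hours from the start of the infusion, and covers 1 of the 10 infusions.

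**2. Whether any text resolves it**

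No section ranks the rules. SAP Section 5 says only that no changes to protocol-specified analyses are planned. Protocol 7.2 asks for capture of events after the first dose but does not define a TEAE. Where the SAP wants a dose-based cut it can write one: Section 4.6.4 separates prior from concomitant medication at the first injection.

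**3. Effect of one subject**

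With 11 per arm (Protocol 6.2; SAP 3.2), one subject whose only related event falls in the window moves the arm by 1/11 = 9.1 percentage points. With exact (Clopper-Pearson) 95% intervals:

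- counted under Section 4.8.1: 1/11 = 9.1% (0.2% to 41.3%)
- counted under Table 5: 0/11 = 0% (0% to 28.5%)

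**4. How likely it is to matter**

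The only data in the documents are in SAP Section 4.9, on the first 4 subjects: "Vital sign measured at Visit 3 and 4 were within normal ranges and no AEs were reported". That is 0/4, exact 95% interval 0% to 60%, so it says little about the rate. It leaves at most 22 − 4 = 18 subjects open to the problem.

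Let p be the chance that a subject has an event that starts after dosing at Visit 3 and is assigned to that visit. Let q be the share of such subjects for whom that event is their only related one. Both are assumed; neither is in the documents.

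- P(at least one subject affected) = 1 − (1 − p)^18
- P(related-TEAE incidence changes) = 1 − (1 − pq)^18

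| p (assumed) | Expected subjects, 18p | At least one affected | Incidence changes, q = 0.5 | Incidence changes, q = 0.25 |
|---|---|---|---|---|
| 2% | 0.36 | 30% | 17% | 9% |
| 5% | 0.9 | 60% | 37% | 20% |
| 10% | 1.8 | 85% | 60% | 37% |
| 20% | 3.6 | 98% | 85% | 60% |

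Every entry is also conditional on Table 5 being the rule that is programmed.

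**The case against.** The best reply is that only Section 4.8.1 defines a TEAE, and the affected tables sit directly under that definition, so a sensible programmer would use it. On this view Table 5 merely sets comparison windows, Section 4.6.3 concerns patient characteristics and excludes nothing from the TEAE tables, and Visit 3 was meant as pre-dose assessment. Protocol 4.2.1 titles the visit as baseline and lists adverse event recording before the infusion, and Protocol 7.2 and 7.3 start reporting at the first dose. All of this is plausible as intent. None of it is written, and Table 5 has a row for TEAEs that is presented as a rule.

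A second reply is that no rule in the documents assigns an event to a visit. An infusion-day event recorded at Visit 4 could count as postbaseline even under Table 5. That is correct, and it is why p above includes assignment to Visit 3.

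A third is that other outputs catch the events, which is largely true. Protocol 6.1.7 and SAP Section 4.8 plan adverse event rates by relation to study drug with no TEAE limit. Serious events and discontinuations due to adverse events are summarised separately, with no baseline window in Table 5. All events are listed. No safety tests are planned. The loss therefore falls mainly on non-serious events that do not lead to discontinuation. The offset is incomplete, because Section 4.8.1 also restricts its serious and early-termination tables to TEAEs, and these could then differ from the separate summaries.

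Finally, the probability range is wide and rests on assumed rates. That also stands: it shows the problem need not be rare, and it does not predict its frequency.

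**Conclusion.** The point holds. Table 5 and Section 4.6.3, as written, class an event that starts after the first infusion begins and is assigned to Visit 3 as baseline. Section 4.8.1 classes it as treatment-emergent, and nothing decides between them.

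The contradiction is certain; its effect is conditional on Table 5 being used and on such events occurring. Where both apply, one subject is enough to shift an arm's related-TEAE incidence by 9.1 percentage points. The direction between arms is unknown, since both are infused. The primary safety endpoint can still be recovered from the adverse event rates by relation to study drug, so it is not lost. What remains is that two planned outputs on related events could disagree for a reason the SAP does not explain. This should be corrected before the final unblinding, so that the rule is not chosen once the results are known.

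**What to change.** - In the TEAE row of Table 5 and in Section 4.6.3, replace the visit cut with the dose cut: a baseline event has onset before the start of the first infusion, and a TEAE has onset at or after it.
- State that Section 4.8.1 governs, and name the first infusion there, since its wording does not say which of the ten doses is meant.
- Add a same-day rule, because Protocol 7.2 records events by start and stop date. An event dated on the day of the first infusion counts as treatment-emergent unless the event description documents that it began before the infusion. Where that information is absent, the default applies.

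The cost is SAP wording only. No new procedure or data field is required; an onset-time field for Visit 3 events would help but is optional. The same-day default may raise the TEAE count slightly, and it applies to both arms alike.
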